- C. Obtaining the voluntary informed consent of individuals to be subjects
- D. Makes decisions about subject eligibility
- E. Studying, interpreting, or analyzing identifiable private information or data/specimens for research purposes
- F. Studying, interpreting, or analyzing de-identified data or specimens for research purposes
- G. Some/all research activities performed outside NIH

Investigational Agents:

Drug Name	GI-6301 Vaccine (Yeast-Brachyury)
IND Number	BB-IND # 14895
Sponsor	NantCell, Inc.
Manufacturer/Supplier	GlobeImmune

Commercial Device: wGT3X-BT manufactured by Actigraph. Associate Investigator in the Diabetes, Endocrinology, and Obesity Branch of NIDDK will provide the actigraphy equipment.

PRÉCIS

Background:

- Chordoma is a rare disease, affecting about 3,000 people in the United States, with about 300 new cases diagnosed per year.
- Brachyury is a member of the T-box family of transcription factors, characterized by a highly conserved DNA-binding domain designated as T-domain.
- Brachyury is expressed universally in chordoma cells.
- GI-6301 (Yeast-brachyury vaccine) has demonstrated immunogenicity with a tolerable and acceptable safety profile in a phase 1 trial.
- Brachyury specific T cells can lyse human cancer cells expressing brachyury in an MHC restricted manner.
- There have been indications of clinical benefit in patients with chordoma enrolled on the phase I trial of GI-6301.
 - 1 **Partial Response**
 - 1 **Mixed Response** in Chordoma patients who received Radiation
 - 6 of 9 patients with progressive disease at enrollment had Stable Disease at Day 85 restaging
- In vitro, chordoma cell lines are killed significantly better by brachyury-specific T cells after radiation exposure using either proton beam or gamma radiation.

Endpoints:

Primary Objective:

- To determine if there is a difference in overall response rate (ORR) defined as complete response (CR) or partial response (PR) by RECIST 1.1 in the irradiated tumor site after up to 24 months among patients with Chordoma who are treated with radiation plus vaccine vs. radiation plus placebo.

Eligibility:

- Patients at least 18 years old with advanced (unresectable, chordoma who are planning to be treated with definitive radiotherapy to at least one lesion.
- No history of autoimmune disease (with exceptions detailed in [section 2.1](#))
- Measurable disease as defined by RECIST 1.1
- Adequate organ function

[figure not shown]
Design:

- Randomized, double-blind, placebo controlled phase 2 clinical trial of radiation plus placebo vs. radiation plus yeast-brachyury vaccine in patients with chordoma.
- Participants will be randomized on a 1:1 basis to the two arms
- Participants assigned to the placebo arm will be allowed to cross-over at time of confirmed disease progression.
- Participants who have had a response in the irradiated target lesion and then have progression outside of the irradiated site will have the option to receive irradiation or other local intervention to the area of disease outside of the radiation field. Progression

will be determined only by the target lesion which had been irradiated. Other lesions will be monitored and intervened upon as clinically necessary. If alternative systemic therapy is required, patients would be taken off study at that point.

- Radiographic progression at the irradiated lesion will be unblinded. Those who did not receive the vaccine will have the option to receive it in combination with radiation to the lesion which is demonstrating disease progression.
- Participants will be evaluated for objective response, and time to progression of the irradiated tumor mass as well as overall survival
- Up to 55 participants will be accrued to the study

Randomization Schema

Primary endpoint: Overall response rate (RECIST 1.1) in the irradiated tumor site(s)

Secondary endpoints:

- Progression free survival (irradiated tumor), PFS (other sites), overall survival
- Patient Report Outcomes

[figure not shown]
Exploratory endpoints:

- Evaluations of response rate and PFS using other criteria
 - (Volumetric, Growth rate kinetics, Choi)
- To evaluate brachyury-specific T cell response pre-, during, and post-treatment.
- To evaluate other parameters of general immune activation detailed in the protocol.
- To evaluate the quantity and quality of tumor infiltrating lymphocytes and other markers of local immune response and inflammation pre- and post-treatment in both groups.
- Daily Activity

Statistical assumption:

- **Goal: improve ORR from 5% to 30%**

Treatment Schema

★ After C7, study agent doses will be given every 3 months (85 days, -7 / +28 days). Restaging scans will be performed at fixed intervals from the time of completion of radiation: 3 months (-7 / +28 days, corresponds to C3D1), 6 months (+/- 4 weeks, corresponds to C6D1), 9 months (+/- 4 weeks, corresponds to C7D1), 12 months (+/- 4 weeks, corresponds to C8D1), 18 months (+/- 8 weeks, C10D1), 24 months (+/- 8 weeks, C12D1), 36 months (+/- 8 weeks, C16D1) and yearly thereafter (+/- 8 weeks). MDASI assessment will take place at baseline and at each restaging imaging timepoint.

8 STATISTICAL CONSIDERATIONS

The primary objective of the trial is to determine if there is a difference in overall response rate (ORR) defined as complete response (CR) or partial response (PR) by RECIST 1.1 in the irradiated tumor site after up to 24 months among patients with Chordoma who are treated with radiation plus placebo vs. radiation plus vaccine.

Based upon results in the literature³⁵, patients who would be eligible to be randomized on this trial would be expected to have an estimated 5% ORR after up to 24 months if treated in a standard manner with radiation alone. The goal of this study will be to determine if the use of radiation along with vaccine will result in patients having an increased response rate by 24 months which is consistent with 30%.

Following the principles of a phase 2.5 design, to compare these two groups and have 80% power to detect a difference between a 5% and 30% 24 month response rate with a 0.10 one-

tailed Fisher's exact test, a total of 25 evaluable subjects per arm (50 total) will need to be randomized over an expected 2 to 3 years, and followed for up to 2 years after randomization.

Patients will be stratified for:

1. Standard fractionation versus hypofractionation radiotherapy dosing
2. Proton versus photon radiation

The vaccine is likely to be very safe, and because the trial is a small randomized phase 2 study, the trial will not require a DSMB to evaluate the findings.

In addition to comparing responses, PFS and OS will be evaluated as secondary endpoints, with Kaplan-Meier curves and a two-tailed log-rank test as the analysis methods. Exploratory evaluations will include response evaluation by other methods, such as Choi and immune-related RECIST criteria (irRC).

It is expected that 20 patients can be accrued onto this trial per year. In order to allow for a very small number of inevaluable patients, the accrual ceiling will be set at 55 patients.

A large black rectangular redaction box covers the majority of the page content, from approximately y=113 to y=885. The redaction is not perfectly uniform, showing some vertical banding and slight variations in tone, particularly towards the bottom right corner where it appears slightly lighter.

A large black rectangular redaction box covers the bottom portion of the page content, starting below the horizontal line and ending at the bottom edge of the page.

12.3 APPENDIX C: TREATMENT AND MONITORING SCHEDULE: PRE, DURING AND POST THERAPY

	Screening	Baseline ¹	C1 D1	C1 D15	C1 D29	Days 43- 100 (+/- 14)	C2 D1	C2 D15	C2 D2 9	C3 D1 – C5 D1	C6 D1 → 2 years on study	Post- treatment follow-up visit
HCG ¹⁰												
Radiotherapy						X						
GI-6301 (Yeast- Brachury Vaccine) or placebo ¹¹			X	X	X		X	X	X	X	X ¹¹	
Yeast allergy test ¹²												
Adverse Events		X		X	X		X	X	X	X	X	
Tissue Samples ¹³		X									X	
Concomitant Medications		X		X	X		X	X	X	X	X	
MDASI		X ³								X ³	X ³	
Actigraphy		X	X	X	X	X	X	X	X			

¹ Baseline: H & P and laboratory studies should be completed within 16 days of initiating treatment. Baseline radiographic, ECOG performance status, EKG and immunologic studies should be obtained within 28 days of initiating treatment.

² Medical assessments: interim history (since last visit), vital signs, physical examination and ECOG performance status, must be performed within 3 days of each dose

³ Radiologic studies consisting of CT chest/abdomen/pelvis and MRI will be performed within 28 days prior to enrollment, after completion of cycle 2 (on or around C3 D1, and every 3 months (-7 days / +28 days) thereafter. After 1 year of SD, PR, or CR, imaging may be performed approximately every 6 months during year 2, and then yearly thereafter. Imaging can be repeated early at the discretion of the investigator/physician. MDASI assessments will take place along with imaging studies.

⁴ Serum HIV antibody should be completed within 12 weeks of initiating treatment. A positive screening test must be confirmed by detectable virus in the serum by PCR.

⁵ Serum hepatitis B & C antibody should be completed within 12 weeks of initiating treatment. A positive screening test must be confirmed by detectable virus in the serum by PCR.

⁶ Chemistry panel: Na+, K+, Cl-, CO₂, glucose, BUN, creatinine, albumin, calcium, magnesium, phosphorus, alkaline phosphatase, ALT, AST, total bilirubin, TSH, and LDH.

⁷ Blood will be obtained for immunologic assays. Research blood will be drawn at baseline and prior to each dose. 2 SST tubes, 6 green top tubes are required.

⁸ ANA and CD3, 4, 8, 19 subsets will be drawn at baseline and prior to C6 D1.

⁹ For patients with questionable history of yeast allergy, this test is performed at the screening visit to detect if the subject has a hypersensitivity to *Saccharomyces cerevisiae*. **A negative response is required for entry into this trial.**

¹⁰ In females of child-bearing age, beta-HCG to be done within 48 hours prior to day 1.

¹¹ Administered subcutaneously at 4 sites. Dosing will be given as follows: on C1 D1, C1 D15, C1 D29 (all +/- 3 days). Dosing will be interrupted for the duration of radiation and will resume 14-28 days post radiation depending on patient schedule and any time required to recover. Treatment is then resumed on C2 D1, C2 D15, C2 D29 (all +/- 3 days). C3 D1 (28 days (+/- 7 days) after C2 D29) begins monthly (28 day +/- 7 days) dosing for 4 doses (cycles 3, 4, 5, and 6). C6 D1 begins every 3 month (85 days -7/+28 days) dosing, which goes on for at least 2 years. After 2 years on study, doses may be given less frequently (every 6-12 months) based on vaccine supply and patient preference

¹³ Performed in subjects with a questionable history of allergy to yeast

¹³ Baseline tissue sample is preferred. These may be fresh biopsy samples or archived tissue. If archived tissue, at least 10 unstained slides are required. On-study biopsy specimens will be analyzed by immunohistochemistry for evidence of immune response within the tumor. These samples may be obtained at 6 or 12 months or at evidence of tumor response or tumor progression. Biopsy is allowable for research purposes at other times at investigator discretion with patient consent to biopsy.

¹⁴ Post-treatment follow-up labs are not required if the subject prefers to follow-up via phone contact.

Abbreviated Title: Ph 2 Yeast-Brachyury Chordoma

NantCell Study number: QUILT-3.011

CC Protocol #: 15-C-0118

OSP#: 1407-1336

Version Date: May 14, 2018

IBC#: RD-15-III-13

Amendment: H

NCT Number: NCT02383498

Title: A Randomized, Double-Blind, Phase 2 Trial of GI-6301 (Yeast-Brachyury Vaccine) Versus Placebo in Combination with Standard of Care Definitive Radiotherapy in Locally Advanced, Unresectable, Chordoma

NCI Principal Investigator:

[name]., NOB, CCR, NCI^{A, B, C, D, E, F}
[name]
[name]
[contact]
Email: [contact]

Sponsor Contact:

[name]
Senior Vice President Adult Medical Affairs
NantKwest Inc.
[name]
[name]
Email: [contact]
[contact]

Investigational Agents:

Drug Name	GI-6301 Vaccine (Yeast-Brachyury)
IND Number	BB-IND # 14895
Sponsor	NantCell, Inc.
Manufacturer/Supplier	GlobeImmune

Commercial Device: wGT3X-BT manufactured by Actigraph. Associate Investigator in the Diabetes, Endocrinology, and Obesity Branch of NIDDK will provide the actigraphy equipment.

STATEMENT OF COMPLIANCE

This trial will be conducted in accordance with Good Clinical Practice (GCP) as described in the International Conference on Harmonization Guideline E6 (ICH E6) and in accordance with United States (US) Code of Federal Regulations (CFR) applicable to clinical studies (45 CFR Part 46, 21 CFR Part 50, 21 CFR Part 56, and 21 CFR Part 312) and the general ethical principles outlined in the Declaration of Helsinki. The study will receive approval from an Institutional Review Board (IRB) prior to commencement. The Principal Investigator will assure that no deviation from or changes to the protocol will take place without prior agreement from NantCell and documented approval from the IRB, except where necessary to eliminate an immediate hazard(s) to the trial participants.

I agree to ensure that all staff members involved in the conduct of this study are informed about their obligations in meeting the above commitments.

Principal Investigator:

Signed: _____ Date: _____

PRÉCIS

Background:

- Chordoma is a rare disease, affecting about 3,000 people in the United States, with about 300 new cases diagnosed per year.
- Brachyury is a member of the T-box family of transcription factors, characterized by a highly conserved DNA-binding domain designated as T-domain.
- Brachyury is expressed universally in chordoma cells.
- GI-6301 (Yeast-brachyury vaccine) has demonstrated immunogenicity with a tolerable and acceptable safety profile in a phase 1 trial.
- Brachyury specific T cells can lyse human cancer cells expressing brachyury in an MHC restricted manner.
- There have been indications of clinical benefit in patients with chordoma enrolled on the phase I trial of GI-6301.
 - **1 Partial Response**
 - **1 Mixed Response** in Chordoma patients who received Radiation
 - 6 of 9 patients with progressive disease at enrollment had Stable Disease at Day 85 restaging
- In vitro, chordoma cell lines are killed significantly better by brachyury-specific T cells after radiation exposure using either proton beam or gamma radiation.

Endpoints:

Primary Objective:

- To determine if there is a difference in overall response rate (ORR) defined as complete response (CR) or partial response (PR) by RECIST 1.1 in the irradiated tumor site after up to 24 months among patients with Chordoma who are treated with radiation plus vaccine vs. radiation plus placebo.

Eligibility:

[figure not shown]
- Patients at least 18 years old with advanced unresectable, chordoma who are planning to be treated with definitive radiotherapy to at least one lesion.
- No history of autoimmune disease (with exceptions detailed in section [2.1](#))
- Measurable disease as defined by RECIST 1.1
- Adequate organ function

Design:

- Randomized, double-blind, placebo controlled phase 2 clinical trial of radiation plus placebo vs. radiation plus yeast-brachyury vaccine in patients with chordoma.
- Participants will be randomized on a 1:1 basis to the two arms
- Participants assigned to the placebo arm will be allowed to cross-over at time of confirmed disease progression.

- Participants who have had a response in the irradiated target lesion and then have progression outside of the irradiated site will have the option to receive irradiation or other local intervention to the area of disease outside of the radiation field. Progression will be determined only by the target lesion which had been irradiated. Other lesions will be monitored and intervened upon as clinically necessary. If alternative systemic therapy is required, patients would be taken off study at that point.
- Radiographic progression at the irradiated lesion will be unblinded. Those who did not receive the vaccine will have the option to receive it in combination with radiation to the lesion which is demonstrating disease progression.
- Participants will be evaluated for objective response, and time to progression of the irradiated tumor mass as well as overall survival
- Up to 55 participants will be accrued to the study

Randomization Schema

Primary endpoint: Overall response rate (RECIST 1.1) in the irradiated tumor site(s)

Secondary endpoints:

- Progression free survival (irradiated tumor), PFS (other sites), overall survival
- Patient Report Outcomes

[figure not shown]
Exploratory endpoints:

- Evaluations of response rate and PFS using other criteria
 - (Volumetric, Growth rate kinetics, Choi)
- To evaluate brachyury-specific T cell response pre-, during, and post-treatment.
- To evaluate other parameters of general immune activation detailed in the protocol.
- To evaluate the quantity and quality of tumor infiltrating lymphocytes and other markers of local immune response and inflammation pre- and post-treatment in both groups.
- Daily Activity

Statistical assumption:

- **Goal: improve ORR from 5% to 30%**

Treatment Schema

★ After C7, study agent doses will be given every 3 months (85 days, -7 / +28 days). Restaging scans will be performed at fixed intervals from the time of completion of radiation: 3 months (-7 / +28 days, corresponds to C3D1), 6 months (+/- 4 weeks, corresponds to C6D1), 9 months (+/- 4 weeks, corresponds to C7D1), 12 months (+/- 4 weeks, corresponds to C8D1), 18 months (+/- 8 weeks, C10D1), 24 months (+/- 8 weeks, C12D1), 36 months (+/- 8 weeks, C16D1) and yearly thereafter (+/- 8 weeks). MDASI assessment will take place at baseline and at each restaging imaging timepoint.

8 STATISTICAL CONSIDERATIONS

The primary objective of the trial is to determine if there is a difference in overall response rate (ORR) defined as complete response (CR) or partial response (PR) by RECIST 1.1 in the irradiated tumor site after up to 24 months among patients with Chordoma who are treated with radiation plus placebo vs. radiation plus vaccine.

Based upon results in the literature³⁵, patients who would be eligible to be randomized on this trial would be expected to have an estimated 5% ORR after up to 24 months if treated in a standard manner with radiation alone. The goal of this study will be to determine if the use of radiation along with vaccine will result in patients having an increased response rate by 24 months which is consistent with 30%.

Following the principles of a phase 2.5 design, to compare these two groups and have 80% power to detect a difference between a 5% and 30% 24 month response rate with a 0.10 one-tailed Fisher's exact test, a total of 25 evaluable subjects per arm (50 total) will need to be randomized over an expected 2 to 3 years, and followed for up to 2 years after randomization.

Patients will be stratified for:

1. Standard fractionation versus hypofractionation radiotherapy dosing
2. Proton versus photon radiation

The vaccine is likely to be very safe, and because the trial is a small randomized phase 2 study, the trial will not require a DSMB to evaluate the findings.

In addition to comparing responses, PFS and OS will be evaluated as secondary endpoints, with Kaplan-Meier curves and a two-tailed log-rank test as the analysis methods. Exploratory evaluations will include response evaluation by other methods, such as Choi and immune-related RECIST criteria (irRC).

It is expected that 20 patients can be accrued onto this trial per year. In order to allow for a very small number of inevaluable patients, the accrual ceiling will be set at 55 patients.

[REDACTED]

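### PFS (other sites): a log-rank test stratified by baseline disease outside the planned radiation field would be a cheap, low-priority improvement on the plain test

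*Combined protocol and SAP*

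**What the plan says.** Section 8 states that "PFS and OS will be evaluated as secondary endpoints, with Kaplan-Meier curves and a two-tailed log-rank test as the analysis methods". The visible text names no strata, covariates or Cox model for these endpoints, and gives no event count, hazard ratio or power for them. The sentence is the same in every version in the file, including Amendment I.

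The Précis lists the time-to-event secondary endpoints as "Progression free survival (irradiated tumor), PFS (other sites), overall survival". Its eligibility summary admits patients "who are planning to be treated with definitive radiotherapy to at least one lesion", and its design summary adds: "Other lesions will be monitored and intervened upon as clinically necessary".

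Randomization is stratified by two factors in Section 8: "Standard fractionation versus hypofractionation radiotherapy dosing" and "Proton versus photon radiation". Both describe the radiation and neither describes the extent of disease.

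Appendix C (12.3), footnote 3, requires baseline imaging: "Radiologic studies consisting of CT chest/abdomen/pelvis and MRI will be performed within 28 days prior to enrollment".

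**The concern.** PFS (other sites) looks only outside the irradiated tumor. A patient with no lesion there at entry can progress elsewhere only through a new lesion. A patient with untreated lesions there can progress through a new lesion or through growth of an old one. The definition of the endpoint therefore makes baseline disease outside the field a natural prognostic factor for it. How strong a factor is not known.

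Two things follow if it is strong. Pooling two groups with very different hazards costs the log-rank test some power, even when the arms are balanced. And with about 25 patients per arm, a chance difference between arms in this factor can shift the p-value and the estimate in either direction. An adjustment chosen after unblinding would look data-driven, so the time to specify it is before.

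**Working it through.** **The plan's own figure.** The only stated power is for the primary endpoint: response 5% vs 30%, one-tailed Fisher's exact test at 0.10, 25 per arm, 80%. Exact enumeration gives 80.7% (78.8% with 24 per arm), so it reproduces. There is no corresponding figure to reproduce for PFS or OS.

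**Inputs.** From the documents: 1:1 allocation, 25 evaluable per arm, a two-tailed log-rank test, and the schema scans at 3, 6, 9, 12, 18 and 24 months after radiation. Assumed, because the documents do not give them:
- two-sided 0.05;
- prevalence of baseline out-of-field disease 10–50%;
- hazard of other-site progression 2, 3 or 5 times higher with such disease;
- placebo median of 12 months in that group;
- vaccine hazard ratio 0.4;
- radiation ending at about month 3, so that events are recorded at months 6, 9, 12, 15, 21 and 27.

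**Chance imbalance.** At 40% prevalence the standard deviation of the arm difference is sqrt(2 × 0.4 × 0.6 / 25) = 0.139, or 13.9 points. A 20-point difference is 5 patients of 25. The exact binomial probability of at least that much is about 3% at 10% prevalence, 11% at 20%, 16% at 30%, 19% at 40% and 20% at 50%.

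**Type I error.** Averaged over all randomizations both tests hold about 5%. Within trials that have the 20-point imbalance, at 30–50% prevalence and 3 to 5 times the hazard, the plain test rejects in 8–14% and the stratified test in 5–7%. A separate simulation with 24 months of follow-up and exponential times gave, for the plain test, about 7% at a prognostic hazard ratio of 2, 9–11% at 3 and 10–13% at 4. The stratified test stayed at about 4–6%.

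**Power, plain vs stratified** (simulated, 4,000 to 9,000 trials per setting):

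| Prevalence | 2× hazard | 3× hazard | 5× hazard |
|---|---|---|---|
| 10% | 52.0% vs 51.3% | 39.8% vs 41.2% | not tabulated |
| 20% | 53.7% vs 54.6% | 42.1% vs 45.1% | not tabulated |
| 30% | 55.3% vs 55.7% | 45% vs 49% | 35% vs 43% |
| 50% | not tabulated | 51% vs 57% | 42% vs 52% |

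With 4,000 trials the standard error of one power figure near 50% is sqrt(0.5 × 0.5 / 4,000) = 0.8 points, so gaps below a point mean little. Over the whole 10–50% range the change is about −1 to +2 points at 2×, +1 to +6 at 3× and +1 to +9 at 5×. The 50%, 5× cell comes out at 9 or 10 points depending on the run. If the factor has no effect, stratifying costs 71.1% − 69.6% = 1.5 points.

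**Sensitivity to the model.** In the separate simulation, at 30% prevalence, treatment hazard ratio 0.5 and a reference median of 24 months, power moved as follows:
- prognostic hazard ratio 1.5: 35.0% to 34.3%;
- 2: 35.6% to 36.8%;
- 3: 35.4% to 39.4%;
- 4: 32.4% to 40.7%.

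The largest gain on its grid was 60.9% to 78.8% (50% prevalence, prognostic hazard ratio 4, treatment hazard ratio 0.4, reference median 10 months).

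**Scale.** By Schoenfeld's formula, events = 4 × (1.960 + 0.842)² / (ln HR)². This gives 66 events for 80% power at HR 0.5 and 38 at HR 0.4. The main simulations produced only about 14–23 events in settings of this kind.

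**The case against.** The strongest reply is that the plan contains no error. A plain log-rank test is valid under 1:1 randomization, PFS (other sites) is a secondary endpoint with no visible power claim, and too few events limits it far more than a missing stratum does. All of that stands, and it is why the point is low priority.

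A reader might infer that chance imbalance will drive the result, or that power is lost as a matter of course. The figures do not support either. The inflated false-positive rate applies only to the minority of trials with a large imbalance and a strong factor. At twice the hazard, or at 10% prevalence, the gain is about −1 to +2 points. The title's restriction to locally advanced disease makes low prevalence plausible. At 10%, the smaller stratum would hold about 5 of 50 patients.

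A reader might also extend the change to the main OS test. Every calculation here concerns other-site progression. No OS event rate or prognostic effect is given or simulated, so replacing that test is not supported.

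Three further cautions stand:
- The sentence about other lesions follows one about progression outside the field after a response, so it may refer to later lesions. The primary endpoint also allows more than one irradiated site. The eligibility summary permits out-of-field disease at entry but does not show how common it is.
- The enrollment scan alone does not classify a patient, because the planned field is needed too. Appendix C puts radiotherapy at days 43–100, and no visible text says the field is fixed at enrollment.
- Section 8 ends in a redacted block, so the point applies only to the visible text.

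The month-27 scan also lies beyond the follow-up of up to 2 years after randomization given in Section 8. With the last scan at month 21, power is roughly 32–46% for the plain test and 36–50% for the stratified test. The direction is unchanged.

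**Conclusion.** The point holds as an inexpensive, low-priority improvement for PFS (other sites) only. The planned test is valid but sets aside a baseline factor that the endpoint's own definition makes relevant and that the two radiation strata do not balance. The benefit is negligible if the factor doubles the hazard or is rare, and becomes material at about three times the hazard with prevalence of 20% or more. There is also some protection in the trials that happen to be badly imbalanced. Prevalence, prognostic strength, vaccine effect and event rate are all assumed, so the ranges show what could happen and are not predictions for this trial. The primary response comparison is not affected.

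**What to change.** In Section 8, for PFS (other sites):
- Make the main comparison a two-tailed log-rank test stratified by disease outside the planned radiation field at baseline (yes/no), and take the hazard ratio from a Cox model stratified the same way.
- Define the factor from the enrollment CT/MRI together with the planned field, classified by someone blinded to arm.
- Keep the plain log-rank test as a sensitivity analysis, and report the factor by arm.
- Do not cross the factor with the two radiation factors: 2 × 2 × 2 = 8 cells is too sparse for 50 patients.

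For OS, keep the plain log-rank test as the main analysis and add the stratified version as a sensitivity analysis only.

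The cost is a few sentences and one derived yes/no variable. It needs no extra patients, visits or scans. The downside is about 1–2 points of power if the factor is not prognostic or is rare.
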